2.2.3 Exploratory

- To assess the effect of combined metformin and doxycycline therapy on the metabolic profile of cancer cells and stroma using mass spectroscopy imaging (MSI) on paired samples, comparing metabolite profiles in the pre-treatment and post-treatment tumor sample.
- To assess the impact of a patient's nutritional status, estimated using 3-day dietary recall versus caloric needs as calculated by the Harris-Benedict equation on the baseline and net change in CAV1. Patients will be labeled as below caloric needs, meeting caloric needs, and exceeding caloric needs.
- To assess the effect of combined metformin and doxycycline therapy on exosome evaluation, metabolomics profile, and microRNA expression profile.

3 Study Design

This is a Phase II parallel cohort design trial in which patients with known or suspected head and neck squamous cell carcinoma who are eligible for resection are randomized to receive either metformin (arm A), doxycycline (arm B), or a combination of those two agents (arm C) in the 1-5 week window of time between their diagnostic or confirmatory biopsy and their tumor resection. All medications should cease at least 12 hours prior to time of resection.

Immunohistochemical analyses will be performed on the pre-treatment biopsy and the post-treatment resection specimens, allowing us to more fully characterize the metabolic microenvironment of HNSCC and our ability to alter it. No patients will receive a placebo. The treatment takes place in a period of time during which no other standard therapy exists for these patients. All patients will be treated at TJUH and all samples material analyzed here with the exception of MSI performed at Vanderbilt. Patient participation will last only during this window of time between enrollment and surgery, up to 5 weeks, with no additional visits planned. Data collected on the patients will include the IHC and MSI on their specimens, serologic assays on their metabolic state, and a characterization of their general nutritional state via the Harris-Benedict equation.

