3.6 Study Timeline

3.6.1 Primary Completion

Eligibility Screening: Trial Coordinator will screen the office charts for possible inclusion in the trial. Labs for the screening part will be available from pre-admission testing that is standard of care for initial biopsy.

Visit 1, Day 0: Subjects that meet the inclusion criteria after reviewing plan for tissue diagnosis, laboratory data and clinical chart will be approached the day of their follow up with a subspecialty surgeon. The initial biopsy does not need to take place on Day 0 and previously obtained tissue may be used. The study coordinator will meet with the prospective candidates and go over the protocol, answer questions and obtain informed consent. Once the subject's laboratory results are reviewed and eligibility is confirmed, the patient will be randomized and metformin and/or doxycycline will be dispensed. Medication will be dispensed from Thomas Jefferson University Investigational Drug Service (IDS) Pharmacy after randomization. Instructions on how to take study drug will be given and times for follow up phone calls for tolerability and safety will be arranged with participants. Patients will also be asked to meet with a nutritionist either in person or by phone within the first 8 days of their enrollment to fill out a 3-day dietary recall log when possible. A nutritionist will either meet with the patients in person or call them within the first 8 days of their enrollment to fill out the 3-day dietary recall log. The nutritionist will do a 2-day guided recall, recording what the patients have eaten in the last 3 days and how much. Two 15 mL vials of blood will be drawn for baseline metabolomics and exosome profiling.

Visit 2, Day of Surgery, Week 1-5 based upon surgery: On the day of surgery, two 15 ml vials of blood will be drawn for post-treatment metabolomic and exosome profiling. A post-treatment tissue sample will be obtained from excess tissue taken from this resection specimen that is not needed in the course of clinical care. On either the day of surgery or up until their first post-op visit, patients will be approached for bottles and pill reconciliation as well as follow up of side effects and adverse events. For patients who, per institutional standard of care, have genetic testing performed on their tumor sample, we will review this information in addition to the remainder of their pathology report.

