5.8 Dietary Restrictions

Subjects should maintain a normal diet unless modifications are required to manage an AE such as diarrhea, nausea or vomiting. Patients will be asked to fill a dietary log at the beginning the study when they speak with a registered dietician.

6 Study Schedule

All patients will be evaluated by a treating surgeon. Initial visit will include overall assessment of health as well as determination of eligibility. A study calendar details the requisite pretreatment evaluations

Study Procedure	Screening	Treatment/Intervention Period ^D						End of ^E Treatment	Follow-up ^G
		Week 1			Week 2 ^D	Week 3-5			
		Day 1 -7			Day 8-14		Surgical ^F Resection	Week 6	Week 7
Administrative Procedures									
Informed consent ^A and research authorization/ HIPAA form	X								
Inclusion/Exclusion Criteria	X								
Demographics, Medical history	X								
Clinical Assessment									
Physical examination, vitals, weight, blood pressure	X							X ^N	x
Height	X								
ECOG Performance status	X								X
Pathology Report histologic confirmation of disease if available ^I	X							X	-
Concomitant meds ^K	X	X	X	X	X	X	X	X	X
Toxicity and AE Assessment ^K	X	X	X	X	X	X	X	x	x

Laboratory tests ^B										
Hematology	X									
Blood Chemistry	X									
pregnancy test ^H	X									
Treatment/ Intervention										
Metformin ^{C,D}		X	X	X	X	X	X			
Doxycycline ^{C,D}		X	X	X	X	X	X			
Diagnostic Biopsy or tumor sample ^I	X							X		
Surgical Resection								X		
Correlative Studies										
Serologic metabolic profile (miR21 and exosomes) ^F		X						X		
Nutrition Assessment*		X ^M								

*Nutrition assessment and Harris Benedict Equation will occur on Day 1 (or up to Day 8) of enrollment when possible, and may be done via a phone interview.

A. Written informed consent must be obtained before any study-specific screening assessments are performed. Lab results performed as standard-of-care prior to obtaining informed consent and within 28 days prior to enrollment may be used; such tests do not need to be repeated for screening. Trial treatment should begin within 5 days of eligibility confirmation.

B. Blood Chemistry includes: Creatinine, AST, ALT, ALK Phos, T Bili $> 2.5 \times$ ULN. Hematology includes: CBC (with differential). All are non-fasting labs.

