C. Study treatment follow up phone calls will occur on days 3 and 5 ± 2 days of dose escalation to evaluate tolerability, document AEs, and concomitant medications. If patient remains on study drugs for >7 days, study treatment follow-up phone calls will occur a minimum of once a week until surgery to evaluate tolerability, AEs, and con meds. Last doses of metformin and/or doxycycline pills should not be taken within 12 hours of scheduled surgery.

D. Patient must receive a minimum of 7 days of metformin and/or doxycycline before having definitive surgery. Patients will stay on metformin and/or doxycycline until the day prior to surgery (up to the maximum of 5 weeks).

E. End of treatment visit may occur within 14 days ± 7 days of stopping study drug.

F. Correlative study blood to be collected the morning of surgical resection. Baseline samples are to be drawn after enrollment but prior to start of study treatment.

- G. Follow up phone call will be performed 30 days after last dose of study medication for any other side effects or toxicity and for pathologic staging information.
- H. serum or urine pregnancy test must be done within 14 days prior to enrollment on study for all women of childbearing potential
- I. If a confirmatory biopsy is performed at TJUH and excess tissue is available tissue will be flash frozen both at the time of biopsy and at the time of resection. A post-treatment tissue sample will be obtained from excess tissue taken from this resection specimen that is not needed in the course of clinical care.
- J. Study drug stopped the night prior to surgery.
- K. Concomitant medication reconciliation, and Toxicity and Adverse Event assessments should be done at every patient contact to fully capture any potential dose limiting toxicities or AEs that affect the patient's ability, willingness, and eligibility to continue taking study medications.
- L. Operative reports should be included with pathology reports in source documents when applicable.
- M. To be performed by a registered dietician, when possible. Must meet with patient within five days of enrollment and record the patient's last 3 days of caloric intake and estimate their caloric intake versus their caloric needs per the Harris Benedict Equation. It will be noted in the patient chart if these assessments could not be completed.
- N. Pre-operative nursing or anesthesia exam is acceptable and is to be performed the morning of surgery.

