6.2 Enrollment/Baseline

- In order to be considered for evaluation, the patient must have an evaluable pre-treatment biopsy specimen.
- If a confirmatory diagnostic core biopsy is required and there is excess tissue available not needed in the course of clinical care, this tissue will be flash frozen in liquid nitrogen.
- Patients who are enrolled in the trial will be randomized to receive metformin, doxycycline, or metformin and doxycycline together. Patients will receive a Patient Medication Diary to record the time (AM and PM) and number of pills taken for metformin and/or doxycycline.
- Baseline caloric intake assessment using a dietary log mediated by a nutritionist when possible. This will take place at the patient's baseline assessment and may be done via a phone interview.

- Calculation of the patient's estimated caloric needs via the Harris-Benedict Equation when possible.
*If the nutrition assessment and Harris-Benedict Equation cannot be completed, this will be noted in the patient's chart.
- Complete physical examination including ECOG performance status, vital signs
- The collection of two serum separator tubes to be drawn after enrollment and prior to the start of the study treatment.
- Concurrent medications will be recorded

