6.6 Withdrawal Visit/Discontinuation of Therapy

Patients can withdraw at any time during the study if they no longer want to participate in the trial. If withdrawal occurs no further metformin and or doxycycline administration will occur and patients will be required to return remaining tablets which will be logged in to medication administration records and destroyed. If a subject withdraws consent to participate in the study, permission will be sought to use data pertaining to the subject in the analysis as far as they participate and they will be removed from subsequent analyses and replaced.

Description of when a subject's participation in the trial may be discontinued:

Specific reasons for discontinuing a subject from this study are:

1. Voluntary discontinuation by the subject who is at any time free to discontinue their participation in the study, without prejudice to further treatment.
2. Safety reasons as judged by the investigator.
3. Severe non-compliance to the protocol as judged by the investigator.
4. Incorrect enrollment of the subject.
5. Subject lost to follow-up
6. Death

7 Study Procedures and Evaluations

Study procedures for this trial include:

- Review and immunohistochemical staining of a patient's diagnostic biopsy, which was performed as standard of care.
- Randomization to receive metformin alone, doxycycline alone, or metformin and doxycycline together.
- Administration of the oral medication(s) listed above as per randomization until the day before the patient's planned surgery.
- The collection of two serum separator tubes to be drawn after enrollment and prior to the start of the study treatment.
- Meeting with a registered dietitian either in person or by phone to do a guided three day dietary recall log within the first 8 days when possible.
- Snap freezing a portion of the patient's biopsy and resection specimen for MSI testing may be performed in a subgroup of specimens.
- Immunohistochemistry on slides from the patient's resection specimen.

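### The baseline 3-day dietary recall is not tied to the first dose, so the exploratory nutrition category may include on-drug days

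*Combined protocol and SAP*

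**What the plan says.** Sections 1.2 (correlative endpoints) and 1.3 present the recall as a description of each patient's metabolic state at baseline, meant to show whether the patient is calorically restricted already. Section 6.2 lists it under enrollment and baseline: "This will take place at the patient's baseline assessment and may be done via a phone interview". Section 2.2.3 uses the resulting three-level label to examine the impact of nutritional status "on the baseline and net change in CAV1".

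The timing is stated in several places, and they do not agree:

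- Section 3.6.1: the nutritionist meets patients or will "call them within the first 8 days of their enrollment to fill out the 3-day dietary recall log". The next sentence reads "The nutritionist will do a 2-day guided recall, recording what the patients have eaten in the last 3 days and how much".
- Section 6, calendar footnote: "Nutrition assessment and Harris Benedict Equation will occur on Day 1 (or up to Day 8) of enrollment when possible".
- Section 6, note M: "Must meet with patient within five days of enrollment and record the patient's last 3 days of caloric intake".
- Section 7, procedure list: "do a guided three day dietary recall log within the first 8 days when possible".

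Study drug is dispensed at Visit 1, after randomization (3.6.1), and note A to the calendar expects treatment to begin within 5 days of eligibility confirmation. Note F and section 6.2 require the baseline blood to be drawn before study treatment starts. Nothing comparable is attached to the dietary recall. Section 11.2 describes no analysis of the nutrition endpoint and no handling of recalls taken after dosing has begun.

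**The concern.** All the timing statements count from enrollment, whereas what makes a measurement a baseline is its position relative to the first dose. A recall that looks back three days from an interview late in the window can describe eating under treatment.

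The protocol itself supplies a route by which treatment could change intake. Section 1.4.1 names minor gastrointestinal upset as the most common metformin toxicity and lists anorexia, nausea, vomiting and dysphagia among reactions seen with tetracyclines. Section 5.8 allows diet to be modified to manage such events.

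A patient who eats less because of the drug could then be labeled as below caloric needs at baseline. Part of any association between that label and the change in CAV1 would reflect tolerance of treatment. The association with baseline CAV1 would also be hard to interpret, because that tissue must predate study drug (4.1.2, exclusion 1) and later intake cannot explain it.

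**Working it through.** The plan gives no figure for this point. Its one computed design figure, 9 evaluable patients per cohort (11.3), reproduces: exact signed-rank power is 86.2% at n = 9 and 80.3% at n = 8, assuming normal change scores with mean 40 and SD 32. The recall does not enter that calculation.

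**Inputs**
- Interview day *d*: 1 to 8 (3.6.1, section 6 footnote, section 7), or 1 to 5 (note M).
- Look-back: three days, taken as days *d* − 3 to *d* − 1.
- First-dose day *k*: 1 to 6, from note A's 5-day allowance.
- Assumptions: enrollment is day 1, eligibility is confirmed that day, and the day of first dose counts as on drug.

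**Formulas**
- Recall wholly on drug: *d* − 3 ≥ *k*, so *d* ≥ *k* + 3. Number of such days: 8 − (*k* + 3) + 1 = 6 − *k* under the 8-day window, and 5 − (*k* + 3) + 1 = 3 − *k* (not below 0) under note M.
- At least one recalled day on drug: *d* − 1 ≥ *k*. Number of such days: 8 − *k*, or 5 − *k* (not below 0) under note M.

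| First dose on day *k* | 1 | 2 | 3 | 4 | 5 | 6 |
|---|---|---|---|---|---|---|
| 8-day window, wholly on drug (of 8) | 5 | 4 | 3 | 2 | 1 | 0 |
| 8-day window, at least one day on drug (of 8) | 7 | 6 | 5 | 4 | 3 | 2 |
| Note M, wholly on drug (of 5) | 2 | 1 | 0 | 0 | 0 | 0 |
| Note M, at least one day on drug (of 5) | 4 | 3 | 2 | 1 | 0 | 0 |

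**Boundary cases**
- A day-1 interview has 0 of 3 on-drug days for every *k*.
- A day-8 interview covers days 5 to 7: 3 of 3 on drug for *k* = 1 to 5, and 2 of 3 for *k* = 6.
- If note M's five days are counted as note A's are here, so that day 6 is allowed, its wholly on-drug counts become 3, 2, 1, then 0 of 6.
- With dosing from day 1 and Table 1 as written, a day-8 recall in the metformin arms covers two days at 1000 mg daily and one at 2000 mg daily. Late recalls are thus not confined to the lowest dose level.

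If the recall is completed before the first dose, 0 of 3 days are on drug in every case.

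**The case against.** **Section 4 may already cover this.** It opens by requiring baseline evaluations before the first dose, and section 6.2 calls the recall a baseline assessment. But section 4 goes on to say that the results of those evaluations are reviewed before enrollment to verify eligibility. The recall takes place after enrollment and is not an eligibility item. If section 4 was meant to include it, it conflicts with the 8-day window, and the text needs the same correction.

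**Permitted days are not patients.** A reader might take 5 of 8 as the share of recalls that will be on drug. The documents do not support that. It is the worst case, with dosing on day 1, and no distribution of interview days is given. The default is early: day 1 in the calendar footnote, and the start of the study in 5.8. First doses can come later under note A, and metformin is also held back around contrast CT (4.1.2, 5.4). This objection stands, and it is why the count is given as a range.

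**The effect on intake is unproven.** Section 1.4.1 calls the metformin upset minor, with cessation in under 5%, and says lower-bowel effects of oral doxycycline are infrequent. The tetracycline list carries no frequencies, and the escalation was chosen to limit side effects. No figure shows that intake would shift enough to move a patient between categories. This also stands.

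**The recall may be meant to show a treatment effect.** Section 2.1.3 lists it under the effect of therapy. Only one assessment is scheduled, however, so it cannot show change.

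**A pre-dose recall would not fully align with baseline CAV1.** Previously obtained tissue may be used (3.6.1), so a gap can remain. That is true, but such a recall would at least be free of study drug.

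**Conclusion.** The point holds as a possible misclassification of one exploratory category. The recall has no pre-dose condition of its own, and both stated windows let on-drug days count as baseline. The interview days giving a wholly on-drug recall range from 0 to 5 of 8, or 0 to 2 of 5 under note M, given the day numbering above and a first dose on days 1 to 6.

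Three stronger conclusions might be inferred and are not supported:

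- *That the measure is contaminated.* The documents show only that it may be. Without interview dates or an effect on intake, the bias cannot be computed.
- *That the main results are affected.* The label does not enter the signed-rank analyses of CAV1 or the secondary markers, nor the sample size.
- *That comparisons between arms are biased.* Side-effect profiles differ and arm C receives both drugs, so unequal misclassification is conceivable. But the plan states it is not powered for between-arm comparisons, and it specifies no between-arm analysis using this label.

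The matter is minor. It deserves correction because the timing statements need reconciling anyway.

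**What to change.** In sections 3.6.1, 6.2 and 7, the section 6 calendar footnote and note M, state one window and require the recall to be completed before the first dose, as baseline blood already is. A telephone interview is already allowed.

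Record the interview date relative to the first dose. In section 11.2, limit the baseline nutrition analysis to recalls with no on-drug days, and use later recalls only in a sensitivity analysis. In the same edit, reconcile the 5-day and 8-day limits, and the 2-day guided recall that is said to cover 3 days (3.6.1).

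The cost is wording, earlier scheduling of a planned contact, and somewhat more missing recalls in a measure already done only when possible. Asking a late interviewee to recall the pre-dose days instead is less attractive. With dosing from day 1, those are days −2 to 0, so a day-8 interview would reach back 8 − 0 = 8 to 8 − (−2) = 10 days.

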6.1 Pretreatment Period/Screening

Screening Assessment (Day -28 to Day -1)

Before initiating any screening activities, the scope of the study will be explained to each patient during informed consent. Patients should be advised of any known risks inherent in the planned procedures, any alternative treatment options, their right to withdraw from the study at any time for any reason, and their right to privacy. After this explanation, patients should be asked to sign and date a Notice of Privacy Practice research authorization/HIPAA form and an IRB-approved statement of informed consent that meets the requirements of the Code of Federal Regulations (Federal Register Vol. 46, No. 17, January 27, 1981, part 50). During the screening period, subject eligibility will be determined according to the inclusion and exclusion criteria (Section 4.1, 4.2). The following assessments will be performed during this time:

- Obtain informed consent and research authorization
- Inclusion/Exclusion Criteria
- Record demographics (including age) and medical history
- Physical exam
- Concomitant meds
- ECOG performance status
- Discuss concurrent medications
- Vital signs [body temperature, blood pressure, pulse, respiratory rate, weight, height]
- Obtain histologic and/or (if appropriate) radiologic confirmation of disease
- Confirm eligibility according to the inclusion/exclusion criteria
- Laboratory tests:
 - Hematology: CBC with differential
 - Blood Chemistry
 - Creatinine, AST, AT, ALK Phos T Bili > 2.5 x ULN (all are Standard Of Care)
 - Serum or urine pregnancy test (within 14 days prior to enrollment for women of childbearing potential)

6.2 Enrollment/Baseline

- In order to be considered for evaluation, the patient must have an evaluable pre-treatment biopsy specimen.
- If a confirmatory diagnostic core biopsy is required and there is excess tissue available not needed in the course of clinical care, this tissue will be flash frozen in liquid nitrogen.
- Patients who are enrolled in the trial will be randomized to receive metformin, doxycycline, or metformin and doxycycline together. Patients will receive a Patient Medication Diary to record the time (AM and PM) and number of pills taken for metformin and/or doxycycline.
- Baseline caloric intake assessment using a dietary log mediated by a nutritionist when possible. This will take place at the patient's baseline assessment and may be done via a phone interview.

- Calculation of the patient's estimated caloric needs via the Harris-Benedict Equation when possible.
*If the nutrition assessment and Harris-Benedict Equation cannot be completed, this will be noted in the patient's chart.
- Complete physical examination including ECOG performance status, vital signs
- The collection of two serum separator tubes to be drawn after enrollment and prior to the start of the study treatment.
- Concurrent medications will be recorded

